Ewald & Wasserman (E&W) will conduct the Aim 3 cluster randomized crossover trial at up to 32 hookah cafés (1 pilot and 31 trial cafés) in Atlanta, GA. This trial will be conducted entirely in the field at the participating cafés. Hookah cafés will be recruited to partner with the research team, which involves allowing participants to be recruited and data collection to occur outside the café prior to café entry and after café exit on at least two data collection periods (across the two trial arms). Cafés must also agree to allow the research team to post health warnings about hookah smoking in the cafés on some of the days of data collection. E&W will be responsible for the recruitment of hookah cafés, hiring of field staff, training of field staff on data collection procedures (in conjunction with the Wake Forest study team), and implementing all data collection procedures. Data collection will involve field research at the hookah cafés. Field staff will approach potential participants before they enter the café to assess interest in the study and eligibility. For those eligible, field staff will complete the consenting process, administer a brief survey on tablet computers, collect expired carbon monoxide breath measurements, and distribute incentives at two time points: before participants enter the café and after they exit. Additionally, field staff will debrief participants at the end of the study. E&W will also be responsible for all participant payments. Finally, E&W will be responsible for printing, implementing, and removing the warning signs at waterpipe cafés.

Methods and Measures

Design

The design of the study is a cluster randomized crossover trial, where the hookah café is the cluster and randomization is at the cluster level. Each hookah café will serve as its own control and will be used for data collection for both study arms: (1) intervention, and (2) control. Each café will start in the no warning control arm to avoid the potential for contamination, since customers may visit the same café on multiple days. In the intervention arm, cafés will display one of four text warnings. In the intervention arm, warning messages will be displayed at various agreed-upon locations in the café, such as on hookah pipes, tables, countertops, walls, and menus. The goal is to maximize the potential for customers to be exposed to warnings.

Setting

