Data collection will occur outside hookah cafés in the Atlanta, GA metro area. Atlanta was chosen as the study site because Georgia's weak smoke-free air law allows smoking in bars and restaurants, including hookah cafés. There are over 100 hookah cafés in the Atlanta metropolitan area and Atlanta is home to 57 colleges and universities. The number of cafés and young adults, and the weak smoke-free air laws make Atlanta the ideal location for this study. We will partner with one pilot café and up to 31 additional cafés to allow study activities, including collecting data with customers before café entry and after café exit, and display of study-produced health warnings about hookah smoking during the times when data collection is occurring. Participants will complete data collection outside of the café at two time points, before entry into the café and after exit from the café.

Subject Selection Criteria

Participants will be those planning to enter a hookah café where the study is being conducted. We aim to have 15 participants complete Time 1 (before café entry) and Time 2 (after café exit) data collection at each café for each arm. In order to account for attrition between time points, we will enroll up to 30 participants at each café during each data collection period. We will schedule data collection periods for when the café is most busy, based on information provided by the café manager or owner.

Inclusion Criteria

- Planning to enter the hookah café where study is being conducted
- Age 18 or older
- English speakers
- Planning to smoke hookah inside
- Planning not to smoke cigarettes, cigars, cigarillos, or marijuana while at the hookah café
- Had not previously entered the café earlier in the day on the same day/night as data collection
- Has not been approached to participate in the study at another café or another day/night at the current café
- Are not employees of the business
- Have capacity to participate as determined by the staff member conducting eligibility screening

Exclusion Criteria

- Not planning to enter the hookah café where the study is being conducted
- Age 17 or under
- Non-English speakers
- Not planning to smoke hookah in the café
- Planning to smoke cigarettes, cigars, or marijuana while at the hookah café
- Are employees of the business
- Has not been approached to participate in the study previously
- Had previously entered the café on the same day/night as data collection

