- Does not have capacity to participate as determined by the staff member conducting eligibility screening

Sample Size

- We will enroll up to 1,560 participants in total, across the 32 cafés (this includes up to 30 participants per night, per café. The goal is 15 **completions** per night, per café).

Interventions and Interactions

Intervention Arm

Study staff will place signs containing a text-only warning (selected from a pool of four warnings on lung damage, heart damage, carbon monoxide poisoning, and stunting fetal growth tested in WT Warnings Aim 2 – IRB00091946) in various locations around the café, as agreed upon with the café owner or designated representative. Locations may include the hookah pipes, tables, interior wall signs, countertop signs, menus,

and bathroom signs (see Figure 1. Table Sign). Sign placement and quantity may differ between cafés. Signs will be removed by study staff at the end of each data collection period.

Control – No Warnings

In the Control arm, there will be no signs placed by the study team at any location within the café.

Data Collection

The timing of data collection periods will be agreed upon in advance between the study team and the café owner, manager, or their designee. When the data collectors first arrive at the café, they will introduce themselves to the café point person and place signs in the agreed-upon locations and will document the locations in the café record (on intervention nights). Additionally, photographs of sign placement will be taken.

The study team will set up tables outside the café, where data collection will be completed. In 2017, we completed a pilot study to test these methods (IRB00044196), which worked well. Data collection will be conducted during café hours, when young adults are most likely to visit waterpipe cafés, based on the advice from café employees. Data collectors will approach individuals before they enter the café to determine interest in the study. Interested individuals may also approach the data collectors. Data collectors will conduct eligibility screening with interested individuals (described above).

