of individuals within study arm within cafés. We let eCO_{ijk} represent the outcome measurement for individual k within study arm j within cluster (café) I , assumed continuous and normally distributed. The model will include a fixed effect for study arm (intervention or control) and random cluster and cluster-arm effects. Models will adjust for individual-level sociodemographics and tobacco use at baseline. In secondary analyses, we will examine the impact of sociability of waterpipe behavior by adjusting models for the number of people with whom the individual is smoking in the café. Secondary analyses will examine the impact of text versus pictorial warnings. These hierarchical models will be fit using PROC MIXED in SAS. Because the intervention effect is estimated within clusters, it is also adequate to model fixed cluster effects but retain random cluster-arm effects. Turner (2007) demonstrated through simulation that these two models perform similarly with 18 clusters with slight differences depending on the degree of correlation. We will examine both approaches as a sensitivity analysis.²² Using the same HLM modeling approach, we will perform analyses on secondary outcomes shown in Table 5.

Human Subjects Protection

Overview

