The study will recruit participants at partnering hookah cafés. Potential participants will be screened for age, intention to smoke hookah, intention to smoke other tobacco products, previous entry into the café before or during the data collection period, current employment with the café, previous encounters with the study team, and capacity to participate. The risks to participants are minimal; the principal risk to participants is the risk of breach of confidentiality. All study data will be entered into databases created on the PHS Surveys website, which is behind the Wake Forest firewall; no data will be stored locally on the tablets. The only personally identifiable information collected is the participant's email, which is to be used for compensation purposes only, which will be linked to their participant ID, but will not be saved or stored with study data. This identifier record will be destroyed upon completion of study activities. Since there is a risk that the tablets may be stolen during data collection, steps will be taken to minimize any potential access to study data. These steps include separating survey data from other data collected during the study, so that the surveys can be opened on a webpage that is not linked to the larger database; enabling remote log-out features on all tables; not storing any data locally on tablets, and not collecting identifiers with study data. There is a possibility that internet access may be lost during data collection. In this instance, the study team will utilize paper forms of all data collection materials. These materials will be locked in a box closely monitored by the study team and will be removed and stored securely after the data collection period has completed. The principal investigator will be responsible for overseeing data and safety risks, although the onsite team will be responsible for day-to-day risk assessment and monitoring. The study team will also submit periodic reports to the Wake Forest Data and Safety Monitoring Board (I-DSMB), per the grant application.

Potential Risks

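### The bar on anyone approached before, combined with the fixed control-first order, selectively depletes frequent patrons on intervention nights, and the primary model names no covariate for it

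*Combined protocol and SAP*

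**What the plan says.** All references are to the combined protocol and SAP.

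- **Subject Selection Criteria, Inclusion Criteria:** a participant "Has not been approached to participate in the study at another café or another day/night at the current café". This covers people who declined or failed screening as well as those who took part.
- **Exclusion Criteria:** the matching item reads "Has not been approached to participate in the study previously". Taken literally it excludes people who have never been approached, so it contradicts the inclusion item. The Overview under Human Subjects Protection lists "previous encounters with the study team" among the things screened for, which supports the inclusion-list reading.
- **Methods and Measures, Design:** "Each café will start in the no warning control arm to avoid the potential for contamination", and the reason given is "since customers may visit the same café on multiple days".
- **Data Collection:** "Data collectors will approach individuals before they enter the café to determine interest in the study". The share of arrivals approached is not given.
- **Analytical Plan:** the primary model has a fixed effect for arm and random café and café-by-arm effects, with no period term. On covariates it says "Models will adjust for individual-level sociodemographics and tobacco use at baseline". How often a person visits this café is not named.

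**The concern.** On a café's first control night, nobody can have been approached at that café before. On a later intervention night, everyone approached there earlier is ineligible. The chance of an earlier approach rises with how often a person comes, so the filter acts mainly on regulars and, within a café, acts after the first control night.

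If regulars smoke more or stay longer, losing some of them lowers the mean eCO boost on intervention nights without any effect of the warnings, and the primary comparison would read this as benefit. The habitual patrons whose behaviour the warnings are meant to change would also be under-represented in the arm that displays them. With one night per arm, a period term could not separate the two effects, because period and arm coincide.

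**Working it through.** **1. The plan's own figure.** Inputs from the Analytical Plan: k = 20 cafés, m = 15 per arm per café, SD s = 30 ppm, ICC r = 0.10 or 0.30, inter-period correlation h = r/2, power 80%. Alpha is not stated; two-sided 0.05 is assumed.

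SE = s × √(2[1 + (m−1)r − mh]/(mk)); detectable difference = (1.960 + 0.842) × SE.

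- r = 0.10: 1 + 1.40 − 0.75 = 1.65; SE = 30 × √(3.30/300) = 3.15 ppm; detectable difference 8.81 ppm (stated 8.81).
- r = 0.30: 1 + 4.20 − 2.25 = 2.95; SE = 30 × √(5.90/300) = 4.21 ppm; detectable difference 11.79 ppm (stated 11.78).

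Both reproduce. The formula treats the two arms at a café as samples of one population and has no term for a shift in who is eligible.

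**2. Size of the shift.** The documents give none of these inputs, so all are assumptions:

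- g, share of regulars among patrons: 0.30 to 0.50.
- x, chance that a regular was approached on the earlier night: attendance 0.25 to 0.50 times approach rate 0.50 to 0.80, so 0.125 to 0.40.
- D, excess eCO boost in regulars: 10 to 30 ppm.
- Occasional patrons are assumed never to have been approached before, and approaches at other cafés are ignored.

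Share of regulars on the second visit = g(1−x)/(1−gx). Spurious difference = (g − that share) × D.

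| g | x | Second-visit share | Fall in share | D = 10 ppm | D = 30 ppm |
|---|---|---|---|---|---|
| 0.30 | 0.125 | 0.2625/0.9625 = 0.273 | 0.027 | 0.27 | 0.82 |
| 0.30 | 0.40 | 0.18/0.88 = 0.205 | 0.095 | 0.95 | 2.86 |
| 0.50 | 0.125 | 0.4375/0.9375 = 0.467 | 0.033 | 0.33 | 1.00 |
| 0.50 | 0.40 | 0.30/0.80 = 0.375 | 0.125 | 1.25 | 3.75 |

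The range is 0.27 to 3.75 ppm, or 3% to 43% of 8.81 ppm, before covariate adjustment.

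**3. Effect on the test.** With bias b, two-sided type I error is Φ(−1.96 − b/SE) + Φ(−1.96 + b/SE). At b = 3.75 ppm it is about 22% for r = 0.10 (b/SE = 1.19) and 14% for r = 0.30 (b/SE = 0.89). At b = 0.27 ppm it stays at about 5%.

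A second set of assumptions in the same formula (regulars 30–70%, approached earlier 10–50%, excess boost 5–20 ppm) gives 0.1 to 3.3 ppm, with type I error up to 18.5% (r = 0.10) or 12.4% (r = 0.30).

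**4. Dependence on order.** Let each earlier night deplete regulars by roughly x. Average depletion by arm is then:

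- control, intervention: 0 and x; gap x.
- C-I-C-I: x and 2x; gap x.
- C-I-I-C: 1.5x and 1.5x; gap about zero.
- C-C-I-I: 0.5x and 2.5x; gap 2x.

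If half the cafés started with the intervention, the second-period depletion would fall equally on both arms and roughly cancel in the contrast.

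**The case against.** Several points on the other side stand.

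- **The rule alone does not bias the arm contrast.** A reader might infer that the bias would survive a balanced order. Depletion in the second period would, but the difference between arms would not. The bias needs the fixed order.
- **Regulars are not shut out.** A reader might infer that regulars are absent from the intervention arm and that the arms sample different populations. Only those approached earlier are lost. In the illustration the share of regulars falls by 3 to 12.5 percentage points.
- **More nights need not make it worse.** The Design section fixes only the starting arm. As step 4 shows, extra periods may leave the gap unchanged, remove it or widen it.
- **Control nights are not exempt.** The inclusion item also bars people approached at another café. With up to 31 trial cafés in one metropolitan area, heavy users who visit several can be screened out on control nights at cafés that join later.
- **Part may already be handled.** The Time 1 survey asks about hookah use, and the model adjusts for baseline tobacco use, which may absorb some of the difference. The survey is listed in the Appendix but not shown, so visit frequency may already be collected.
- **The upper figure stacks extremes.** It takes the top of every range, and a 30 ppm excess equals the whole assumed SD.

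Excluding earlier participants is defensible, since they are debriefed on the study's purpose. That reason does not extend to people who declined or failed screening. Not approaching them again is still a reasonable choice, because admitting them only on later nights creates an asymmetry of its own.

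**Conclusion.** The point holds as a modest, cheaply addressed weakness. The eligibility wording, the fixed control-first order and the expected repeat visits together make frequent patrons more likely to be screened out on intervention nights than on a café's first control night. No named covariate or planned report addresses this directly.

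The mechanism follows from the text; the size does not. Under the stated assumptions the spurious difference is about 0.3–3.8 ppm in favour of warnings before adjustment. That is below the 8.81 ppm detectable difference throughout, negligible at the low end, and enough at the high end to inflate type I error materially. If regulars have a smaller boost than other patrons, the sign reverses. The documents do not support a reading in which a positive result would be explained by this selection alone.

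**What to change.** 1. Record at Time 1, if the survey does not already do so, the number of visits to this café in the past 30 days. It is asked before entry, so that night's signs cannot affect it.
2. Name that count as a covariate in the primary eCO model in the Analytical Plan. Because regulars are depleted and not absent, both arms should still contain frequent visitors, so the adjustment is workable.
3. Report by arm the number of people screened out for prior approach or prior participation.
4. Reconcile the inverted exclusion item with the inclusion item.

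The sponsor could also consider limiting the bar to people who enrolled earlier. If, by assumption, half of those approached enrol, x falls from 0.40 to 0.20. At g = 0.50 the second-visit share is then 0.40/0.90 = 0.444, and the largest bias falls from 3.75 to 0.056 × 30 ≈ 1.7 ppm. The price is that earlier decliners could enter only on later nights, so this is an option and not a clear gain.

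The cost is at most one added survey item, one covariate and one line of screening counts. The covariate corrects the imbalance only in part: regulars who were missed earlier may differ from equally frequent regulars who were approached.

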The goal of the overall grant is to develop warnings to promote greater understanding of harms and to reduce WTS behavior among young adults. We have used a systematic, evidence-driven, rigorous approach to develop waterpipe warnings and test these newly developed warnings in two contexts: (1) on waterpipe tobacco packaging; and (2) in an ecologically valid waterpipe café setting. In Aim 1, we developed text and pictorial waterpipe tobacco warnings to effectively communicate a broad range of health harms. We first developed 30 text warnings based on three themes: acute health harms, chronic health harms, and correcting misperceptions. We tested these warnings in a national survey to determine the five most effective text warnings (IRB00062703). We then selected three illustrative images of the health effects presented by the warnings for each of these warnings, plus the federally mandated nicotine warning. We conducted an experiment to determine the most effective image for each of the six warning messages (IRB00080199). In Aim 2 (IRB00091946), we compared the effects of pictorial warnings versus the text-only warnings and a no-warning control placed on fictional packaging on WTS intentions.

Warning placement on packaging and at the point-of-sale is typically the result of legal mandates. In order to approximate the impact of a legal mandate to require health warnings at the point-of-sale, we will partner with places that sell waterpipe tobacco for use onsite. These places may be cafés, restaurants, lounges, bar, etc. (herein referred to as “hookah cafés”). Conducting an experiment where hookah café customers are exposed to waterpipe warnings will allow us to test the impact of the warnings on actual behavior, in the absence of legal mandates. In this experiment (Aim 3), we will conduct a cluster randomized crossover trial with up to 32 hookah cafés in Atlanta, GA (1 pilot and 31 trial cafés). We plan to overenroll cafés to account for dropout/early termination. The goal is at least 20 cafés with 15 participants per arm. Each café will serve as its own comparison as it cycles through the two trial arms: intervention (text warning) and control (no warning). The pictorial warning condition was removed in July 2024 after consultation with E&W and NCI regarding unwillingness of cafés to allow placement of pictorial warning signs. We will randomly select one of four health warning messages from Aim 2 to be displayed in each of

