Data collectors will also make a determination, based on their interaction with the participant, of the participant's capacity to participate in the study. If they determine that the person does not have capacity, they will mark this on the Eligibility Form and the participant will be Not Eligible. If they determine that the person does have capacity, they will mark the participant such on the Eligibility Form and will continue with the Consent process. Determination of capacity to participate will be based on whether people can adequately answer the eligibility screening questions. Eligible participants will be read the consent information by a data collector prior to enrollment and provide verbal consent. A printed consent document will be available for participants if they ask to see it.

After completing the consent process, participants will be given a wristband with their participant ID. Then, they will complete a brief survey about their hookah use behaviors, demographics, and recent use of other combustible products. They will enter their email into a Qualtrics link managed by Ewald & Wasserman to receive their first (\$25) electronic gift card; this is not stored with study data, although it is linked to PID. Next, participants will provide up to two samples of expired carbon monoxide (eCO) by blowing into a carbon monoxide (CO) monitor. This non-invasive process involves taking a deep breath, holding it for 15 seconds, and then exhaling into a sterile tube until the lungs are completely empty. Expired CO is a well-established measure of tobacco smoke exposure. Participants will then be able to enter the café as planned. All participants will be asked to return to the data collectors after exiting the café to complete the follow-up measures. If the data collection period is scheduled to end before the café closes, data collectors will instruct the participants to come outside for Time 2 measures before the data collection period will end. Upon exiting the café, participants will complete a similar brief survey, provide their email again for their second (\$50) compensation, and provide up to two new samples of eCO, using the same procedure as described above. Participants will be debriefed on the purpose of the study and the CO measure. The debrief form will also have resources for more information about CO and health harms of hookah smoking, and contact information for the study PI, the Wake Forest IRB, and E&W for assistance with compensation.

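### A café's control and intervention visits are not required to match on weekday, start time or length, so night type and period length can be confounded with arm

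*Combined protocol and SAP*

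**What the plan says.** In the combined protocol and SAP, the Data Collection section (under Interventions and Interactions) sets timing as follows: "The timing of data collection periods will be agreed upon in advance between the study team and the café owner, manager, or their designee". Two rules narrow the choice, and both apply to either arm:

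- Subject Selection Criteria: "We will schedule data collection periods for when the café is most busy, based on information provided by the café manager or owner".
- Data Collection: "Data collection will be conducted during café hours, when young adults are most likely to visit waterpipe cafés, based on the advice from café employees".

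No section asks that the two arms' periods at one café fall on the same weekday, start at the same time or last equally long. Other provisions bear on this:

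- **Contrast.** The opening background section says: "Each café will serve as its own comparison as it cycles through the two trial arms".
- **Order.** Under Design: "Each café will start in the no warning control arm to avoid the potential for contamination, since customers may visit the same café on multiple" (quote cut before its last word).
- **Number of visits.** The Roles section asks each café for two or more periods in total over both arms, so an arm may be one night.
- **End of period.** Data Collection adds a rule for early finishes: "If the data collection period is scheduled to end before the café closes", participants are told to come out for Time 2 before it ends.
- **Model.** The Analytical Plan specifies a fixed arm effect, random café and café-arm effects, and individual-level covariates. It notes that café-level covariates could be included but names none. Weekday, hour and period length do not appear.

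**The concern.** Using each café as its own comparison removes only what is stable about the café. Whatever differs between its two nights stays in the contrast, and with one night per arm it cannot be separated from the warning within that café. Across cafés, such differences cancel only if they have no net direction. Because control always comes first, no random allocation assigns nights to arms and so balances night type.

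Period length is the clearest route, because the plan itself supplies it. A period that closes early cuts short the time available to smoke, and the primary outcome is the change in eCO from entry to exit. Weekday and hour are plausible further routes, but the documents give no data on them. If control visits tended to be the longer or heavier nights, the warning would look more effective than it is. The opposite tendency would hide a real effect.

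**Working it through.** **Inputs from the Analytical Plan:** K = 20 cafés, m = 15 completers per arm, SD s = 30 ppm, ICC r = 0.10 or 0.30, inter-period correlation h = r/2, power 80%. Alpha is not stated; two-sided 0.05 is assumed.

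**1. The plan's own figure.**

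SE = sqrt{ (2s²/(Km)) × [1 + (m−1)r − mh] }, where 2s²/(Km) = 1800/300 = 6. Minimum detectable difference (MDD) = (1.96 + 0.8416) × SE.

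- r = 0.10, h = 0.05: SE = sqrt(6 × 1.65) = 3.146, MDD = 8.81 ppm.
- r = 0.30, h = 0.15: SE = sqrt(6 × 2.95) = 4.207, MDD = 11.79 ppm.

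The plan states 8.81 and 11.78, so its figures are reproduced (11.787 truncated rather than rounded).

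**2. What the plan already allows for.** Setting h below r implies a café-by-period component with SD = sqrt[(r − h) × 900]. This is sqrt(45) = 6.7 ppm at r = 0.10 and sqrt(135) = 11.6 ppm at r = 0.30. Random variation between a café's two visits is thus in the sample size, and the random café-arm effect puts it in the analysis.

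**3. Undirected mismatch beyond that allowance (illustration).** Let a share p of cafés have visits differing by ±D ppm with no preferred sign. This adds pD²/K to the variance. For p = 0.5 and D = 10 it adds 0.5 × 100/20 = 2.5.

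- r = 0.10: SE = sqrt(9.9 + 2.5) = 3.52, MDD 9.87 ppm, power at the planned difference 70.7%.
- r = 0.30: SE = sqrt(17.7 + 2.5) = 4.49, MDD 12.59 ppm, power 74.6%.

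If h = r/2 already covers such mismatch, this loss does not arise.

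**4. Sensitivity to h (illustration).** With h = 0.75r the MDD is 7.75 ppm (r = 0.10) or 9.27 ppm (r = 0.30). With h = 0.25r it is 9.77 or 13.85 ppm. Nothing in the documents says how far matching would move h.

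**5. Directional mismatch (illustration).** Let D be the difference in mean eCO boost between heavier and lighter nights, and q the net share of cafés whose control visit falls on the heavier one. Bias = D × q. The two-sided false-positive rate under no warning effect is 1 − Φ(1.96 − bias/SE) + Φ(−1.96 − bias/SE), with the SE from step 1.

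| D (ppm) | q | Bias (ppm) | False-positive rate, r = 0.10 | False-positive rate, r = 0.30 |
|---|---|---|---|---|
| any | 0 | 0 | 5% | 5% |
| 5 | 0.25 | 1.25 | 6.8% | 6.0% |
| 10 | 0.25 | 2.5 | 12.5% | 9.1% |
| 15 | 0.25 | 3.75 | 22.2% | 14.5% |
| 5 | 0.50 | 2.5 | 12.5% | 9.1% |
| 10 | 0.50 | 5.0 | 35.6% | 22.1% |
| 15 | 0.50 | 7.5 | 66.4% | 43.0% |

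Over the nonzero rows the bias runs from 14% to 85% of the 8.81 ppm MDD, and from 11% to 64% of the 11.79 ppm MDD. D and q are assumptions; the documents give neither.

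**The case against.** The case on the other side has real weight.

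- **The scheduling rules bind both arms.** Busy times and young-adult hours narrow the range of nights, and the target of 15 completions discourages quiet ones. This stands, but two busy nights can still differ in weekday, hours and length.
- **Random night variation is already budgeted** through h = r/2 and the café-arm effect. This stands in full, so the precision argument alone would not carry the point.
- **The bias depends on the fixed order.** If both dates were set first and the order then randomized, night type would balance in expectation. This is largely right, but the plan fixes the order, and matching helps whatever the order.
- **Time in the café is already measured.** It is, but the warning may itself shorten the stay, so adjusting for it could remove part of the effect. Scheduled period length does not have that problem to the same degree.

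A reader might go further and infer that owners choose the night and steer the sign visit to a slower or shorter one. The documents do not support this. Timing is agreed jointly, a slower night would go against the busy-time rule, and the unwillingness recorded in the background section concerned pictorial signs, since removed. Participating cafés must agree to warnings being posted. That a café can tell which visit carries signs is a fair inference from the fixed order and from placement "in various locations around the café, as agreed upon with the café owner or designated representative", but it shows only that influence is possible.

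**Conclusion.** The gap is real and should be closed. The plan has no rule matching a café's two visits on weekday, start time or length, and no model term for them. With a fixed order and possibly one night per arm, these features can be confounded with the warning.

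Two stronger conclusions do not follow. It cannot be said that every café's contrast is confounded, because mismatch is permitted, not prescribed. Nor can it be said that the estimate will be biased, because that needs a net direction across cafés, which no passage shows. The size of any bias cannot be derived from the documents. The 1.25 to 7.5 ppm range rests on assumed night-type differences of 5 to 15 ppm with a net 25% to 50% of cafés imbalanced, and the figures for other values of h are likewise illustrations, not a forecast of what matching would gain.

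**What to change.** In Data Collection, state that:

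- within each café the control and intervention periods are held on the same day of the week, with the same start and end clock times, wherever the café allows;
- if an arm has more than one period, the set of weekdays and hours is matched across arms;
- both arms' dates are agreed before the first visit and lie close together in time;
- where only the control visit has been done, the intervention visit is matched to it.

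Record weekday and actual start and end times in the café record. In the Analytical Plan, add a sensitivity analysis restricted to matched cafés, or one adjusting for weekday and scheduled period length. With one period per arm, 20 cafés give only 20 × 2 = 40 café-periods, so any weekday term must be coarse.

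The change needs no added visits or staff by design. It costs some scheduling flexibility with cafés. Returning on the same weekday soon afterwards may also meet more patrons who were approached at the first visit and are therefore ineligible, which could slow recruitment at the second.
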